2.3 Exclusion criteria

Parental objection to use of their child's data in the study.

2.5 Outcomes

2.4.1 Primary outcomes

The two co-primary outcomes are:

1) Death or moderate-or-severe neurodevelopmental disability (NDD).

A child will be classified with moderate-or-severe NDD if any of the four following conditions are present:

- cerebral palsy with functional impairment corresponding to Gross Motor Function Classification Score (GMFCS) ≥ 2 ;
- a score below -2 standard deviations from the norm of a standardised developmental assessment (if using the Bayley III/IV test, the cognitive score cut-off will be < 85), or an informal classification of moderate-or-severe NDD;
- vision impairment defined as moderately reduced vision, or only being able to perceive light or light reflecting objects; or blind in one eye with good vision in the contralateral eye.
- hearing impairment defined as hearing loss corrected with aids (usually moderate 40-70dBHL) or some hearing loss not corrected by aids (usually severe 70-90dBHL).

2) Bayley III/IV mean cognitive score

2.4.2 Exploratory outcomes

The exploratory outcomes are as follows:

- Daily medication the last two months (yes/no)
- Any other chronic illness (defined as any problem which has been diagnosed by a doctor and which 1) is expected to last more than a few months, 2) causes problems in everyday life, or 3) is a risk of early death or disability)
- Mean head circumference
- Mean height
- Mean body weight, with one decimal

All components of the co-primary outcomes will be reported for the two groups separately as well as effect estimates with confidence intervals and will be taken into consideration when interpreting the main results

All outcomes will be assessed from health care records by a blinded assessor at a minimum of 12 months of corrected age.

2.6 Outcome assessment tools

The following outcome assessments tools may be used to collect data on children in the SafeBoosC III follow-up study. We aim to collect data on as many children as possible and will do this by collecting clinical data from health care records as well as answers from parental questionnaires.

2.6.1 The Bayley assessment

The Bayley Scales of Infant Development (Bayley) is a commonly used neurodevelopmental assessment tool for children from 1 to 42 months of age (32). There now exists a second (Bayley II), third (Bayley III) and fourth (Bayley-IV) version. The Bayley II measures a Mental Developmental Index (MDI), which is based on a composite of early cognitive and language development, as well as a Psychomotor Development Index (PDI), which assesses motor abilities (33). In the revised Bayley III (2008), the two indexes, MDI and PDI, were replaced by five individual subcategories: cognitive, language, motor, social-emotional and adaptive behaviour (34)..

The correspondence between the Bayley II and III has been examined in previous studies (12, 34, 35). Bayley III scores are approximately 10 points higher than the Bayley II, thus resulting in less infants being diagnosed with neurodevelopment impairment using conventional cut-offs (-2SD). This has implications for both clinical practice as well as research, where the underestimation of neurodevelopmental impairment may lead to reduced statistical power in randomised trials. Some NICUs may switch to the Bayley-IV during the SafeBoosC-IIIIfu study. In published data from Pearson (52) it is argued that there is evidence to support the accuracy and validity of the Bayley-IV scores. Furthermore, as the Bayley-IV (2019) retains the same subcategories and assessment methods as Bayley III, it predicted yield similar scores to the Bayley III. No randomised clinical trials have used and published results using the Bayley IV as an outcome measure yet, and therefore the scores will be treated equal to the Bayley-III scores in the co-primary outcome Bayley III mean cognitive score. In the event of a possible difference between the Bayley III and IV scores, the nature of a randomised trial and block randomisation will equally distribute the differences between the experimental and control group. Furthermore we will conduct a sensitivity analysis investigating a possible influence on treatment effect caused by differences in Bayley III and IV scores.

For the purpose of the co-primary outcome Bayley III/IV mean cognitive score, the unadjusted mean scores from the experimental and control group will be compared. If the Bayley III/IV cognitive score is used to evaluate cognitive function in co-primary outcome death or moderate-or-severe NDD, the cognitive function cut-off will be <85 , as done in previous trials and recommended by experts (35).

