3.1 Primary analyses

The primary analysis of all outcomes will be based on the intention-to-treat population. Mixed-effect linear regression and mixed-effect logistic regression will be used to analyse the dichotomous and continuous co-primary outcomes, respectively. Data from all participating sites will be used in the primary analysis of both co-primary outcomes. In the regression models, 'site' will be included as a random effect, while 'gestational age below or above 26 weeks of postmenstrual age' and 'group allocation' will be included as fixed effects. To correct for multiple testing, the threshold for statistical significance will undergo Bonferroni adjustment, and thus a p-value of 0.025 for each primary outcome is chosen. Superiority of the intervention will only be claimed if at least one of the two co-primary outcomes is statistically significant. All other outcome results will be considered hypothesis-generating only. In addition, we will perform a range of pre-defined sensitivity analyses to inform the interpretation of the results of the primary analysis. A full statistical analysis plan will be developed and submitted for publication before the analysis of the SafeBoosC-III trial data.

[figure not shown]

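### Sections 2.6.1 and 3.1 give two unreconciled descriptions of the Bayley III/IV co-primary comparison; 2.6.1 should say what *unadjusted* means and point to the 3.1 model

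*Combined protocol and SAP*

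**What the plan says.** Section 2.6.1 (The Bayley assessment), within the part on outcome assessment tools, closes with a statement about the Bayley co-primary: "the unadjusted mean scores from the experimental and control group will be compared". It does not say for what the means are unadjusted, and it does not refer to section 3.1. The text just before it concerns differences between Bayley editions and decides that for Bayley-IV "the scores will be treated equal to the Bayley-III scores in the co-primary outcome Bayley III mean cognitive score". The sentence just after it turns to the dichotomous co-primary, for which "the cognitive function cut-off will be <85 , as done in previous trials and recommended by experts".

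Section 3.1 (Primary analyses) sets out the models. For the random part it states: "In the regression models, 'site' will be included as a random effect". The other covariate and the treatment term are listed separately: "gestational age below or above 26 weeks of postmenstrual age' and 'group allocation' will be included as fixed effects". It covers both outcomes: "Data from all participating sites will be used in the primary analysis of both co-primary outcomes". On significance, "a p-value of 0.025 for each primary outcome is chosen", and success on one co-primary is enough to claim superiority. The sentence that assigns models to outcomes reads: "Mixed-effect linear regression and mixed-effect logistic regression will be used to analyse the dichotomous and continuous co-primary outcomes, respectively".

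**The concern.** A comparison of unadjusted group means, in ordinary trial usage, has no covariates. The section 3.1 model has two terms besides treatment. Both sections speak of the same outcome and the same two groups, so a reader who takes each at its word has two descriptions of one comparison.

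This outcome can carry a superiority claim by itself at 0.025, so its analysis should be unique and fixed before data are seen. If the literal reading of 2.6.1 were followed, the analysis would also give up the precision that site and gestational age provide. The model sentence in section 3.1 does not remove the doubt, because its word order gives the continuous outcome a logistic model. Read literally, the plan never assigns a linear model to the Bayley score.

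**Working it through.** **1. The plan's own figure.** Inputs from section 3 (Bayley power calculation): difference 5, SD 20, 425 per group, alpha 2.5%. Sidedness is not stated; two-sided is taken because it fits.

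- SE = 20 × √(2/425) = 1.372
- 5 / 1.372 = 3.644; critical value z(0.9875) = 2.241
- Power = Φ(3.644 − 2.241) = Φ(1.403) = 92.0%

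This agrees with the stated 90% to within two points. One-sided 2.5% would give 95.4%, a poorer match. The calculation has no term for site or gestational age, so it describes the unadjusted comparison.

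**2. The same calculation with covariates.** Let R² be the share of score variance explained by site and gestational-age stratum. The documents give no value, so 5% to 20% is assumed. Adjusted SE = 1.372 × √(1 − R²), taking the arms as balanced within site and stratum.

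| R² (assumed) | Adjusted SE | Unadjusted SE larger by | Power at 5 points |
|---|---|---|---|
| 0 | 1.372 | – | 92.0% |
| 5% | 1.337 | 2.6% | 93.3% |
| 10% | 1.302 | 5.4% | 94.5% |
| 20% | 1.227 | 11.8% | 96.7% |

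The literal reading of 2.6.1 costs 1.3 to 4.7 points of power, and neither reading falls below 90%.

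**3. How often the verdicts differ.** Both tests were applied to the same simulated trials: 850 children, 40 sites, SD 20, half the children in each gestational-age stratum, R² of 5%, 10% or 20% (60% of it from site, 40% from gestational age), 4,000 trials per setting. All of these except 850 and SD 20 are assumptions. The adjusted test used fixed site effects as a stand-in for the random effect.

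| Allocation | Verdicts differ at 0.025, true difference 5 | At least one test below 0.025, no true difference |
|---|---|---|
| Blocks of four within site and stratum | 1.3% to 2.5% | 2.7% to 2.9% |
| Simple | 3.4% to 5.6% | 3.2% to 4.2% |

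The simulation error on a 2.5% rate is √(0.025 × 0.975 / 4,000) = 0.25 points, so the blocked result under no difference is hardly distinguishable from nominal.

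At smaller true differences the verdict is closer to the line. With 3 to 4 points, blocked allocation, a site intraclass correlation of 0.05 to 0.10 and 4 to 6 points between strata (all assumed), the tests disagreed in about 3% to 6% of trials.

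**4. The passages side by side.** Section 2.6.1 names an outcome and a comparison, but no test, model or threshold. Section 3.1 names the model, the covariates and the threshold, and is headed as the primary analysis. The two are compatible if *unadjusted* refers to the scores (no correction for test version). They are incompatible if it refers to the comparison (no covariates).

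**The case against.** The strongest reply is that there is no conflict. The paragraph before the sentence is about shifts between Bayley editions, and the sentence after it sets a cut-off chosen because of such a shift. In that sequence *unadjusted* naturally means raw scores. The sensitivity analysis planned in 2.6.1 for Bayley III versus IV fits this: raw scores in the main analysis, the effect of version examined separately. Section 3.1 is also the only place that designates a primary analysis. This stands as the more likely intention. It does not make the sentence clear: version handling has already been settled by then, and the word is attached to group means that are to be compared.

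A reader might infer that the plan contains two rival primary analyses, each tested at 0.025. The documents do not support that. Section 2.6.1 never calls its comparison primary and attaches no threshold to it.

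A reader might also infer that the team could choose whichever result is favourable. The plan limits this: section 3.1 promises a full analysis plan, submitted for publication before the trial data are analysed, and section 3.2 has two blinded statisticians analyse independently, with both reports published. Those safeguards do not define the word, but they leave little room for selection by result.

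Finally, it is tempting to say that the unadjusted standard error is simply too large. That requires arms balanced within site and stratum. Section 2.6.1 mentions block randomisation only, and nothing here states that it was done within site or gestational-age stratum.

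**Conclusion.** The point holds as a matter of wording that needs reconciling. Two sections describe the comparison for one co-primary differently, and the word that separates them is undefined.

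The size is small. Power is above the stated 90% on either reading. At the planned 5-point difference the two analyses would disagree at 0.025 in roughly 1% to 2.5% of trials under blocked allocation. This rests on assumed variance shares, an assumed number of sites, and assumed blocking within site and stratum; with simple allocation the figure would be about 3% to 6%. The loss of precision under the literal reading is likewise conditional on balance within site and stratum.

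The clearer error is in section 3.1 itself: the *respectively* sentence pairs each co-primary with the wrong type of model. It is evidently a slip, but it sits in the sentence on which the resolution of 2.6.1 depends.

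**What to change.** In section 2.6.1, replace the sentence on unadjusted means with wording such as: *Bayley-III and Bayley-IV cognitive scores are entered as recorded, without correction for test version. The groups are compared with the mixed-effect linear model of section 3.1, which is the only primary analysis of this outcome; unadjusted group means are reported descriptively.*

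In section 3.1, reverse the pairing so that mixed-effect logistic regression goes with death or moderate-or-severe NDD and mixed-effect linear regression with the Bayley score. Carry both changes into the full statistical analysis plan.

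The cost is two edited sentences. No data, sample size or procedure changes, and the model kept is the one the plan already specifies.

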2.6.2 Medical examination

A medical examination will ideally include measurement of head circumference, height and weight, and the child's vision and hearing will be tested, either formally or informally. Signs of cerebral palsy is usually be documented as well as motor abilities (40). Furthermore, the presence of chronic illnesses and/or medication usage will be obtained from medical records.

2.6.3 Parental questionnaires

The parental questionnaires will be comprised of the PARCA-R and a health and development questionnaire.

2.6.3.1 PARCA-R

The Parent Report of Children's Abilities – Revised (PARCA-R) is a parental questionnaire that can be used to assess children's non-verbal cognitive and language development at 24 months' corrected age. The PARCA-R provides a high test-retest reliability and correlates well with the Mental Development Index (MDI) of the Bayley II, and with the cognitive score of the Bayley III (28, 36, 37). The questionnaire has been used as a two-year outcome measure in multiple clinical trials (29) and has furthermore been translated into several languages. For this follow-up study, an online platform will be developed, where parents of the participating children will be invited to complete the non-verbal cognitive (NVC) part of the PARCA-R questionnaire, in their respective languages. This typically takes less than 15 minutes to complete (38). The full PARCA-R will not be used, since a validated language component is not available in all countries; PARCA-R has only been standardised for use in the UK. The PARCA-R must be assessed on children between 23.5 and 27.5 months of corrected age. Children will be classified as having moderate-or-severe NDI when scores correspond to a scale score of -2SD from the norm (39).

The NVC scale consists of 34 forced-choice items, scored zero or one, from which a total NVC score is derived, which is adjusted for the child's corrected age. In cases where no physical standardised assessment (i.e. Bayley, Griffiths etc) of the child is available, NVC cut-off scores will be used as the measure of cognitive function for the co-primary outcome death or moderate-or-severe NDD. When more than four items are missing, the NVCs will not be calculated, but will be categorised as "unknown."

2.6.3.2 Health and development questionnaire

The PARCA-R questionnaire will be supplemented with a number of health and developmental questions to be answered by the parents as well. The questions focus mainly on the individual components of the moderate-or-severe NDD outcome definition, as well as quality of life questions. It will be available on the online platform as well. The coding of the health and development questionnaire for the co-primary outcome moderate-or-severe NDD can be found in Appendix B.

2.7 Data extraction

All data extraction from health care records and data entry into the e-CRF will be done by an assessor who is blinded to group allocation (see section '2.8 Blinding'). The co-primary outcome

Bayley III/IV mean cognitive score will be extracted from the records of the Bayley III/IV test. The co-primary outcome death or moderate-or-severe NDD will primarily be based on an assessment of available health care records, from when the child was between 18 and 30 months' corrected age. If more than one formal neurodevelopmental assessment has been conducted, the score of the latest should be used. If formal assessment of all four components is not available, the central trial unit will substitute the missing components with answers from parental questionnaires (PARCA-R and health and development questionnaire). The answers from the questionnaires will be reported directly by the parents to the central trial unit. If answers from parental questionnaires are not available, either the PI will be contacted by the central trial unit and requested to provide an informal assessment of the presence or absence of moderate-or-severe NDD. The assessment should be based on all available information from the child from at least 12 months' corrected age. For additional details on this approach, see appendix A.

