Appendix A: Prioritisation of data for the co-primary outcome moderate-or-severe NDD

NDD = moderate-or-severe neurodevelopmental disability = positive findings for at least one of the four components or NDD based on an informal blinded assessment of all available information

No NDD = no moderate-or-severe neurodevelopmental disability = no positive findings in any of the four components and no NDD based on an informal blinded assessment of all available information

Unclassifiable = if one or more components are unknown and none are positive and there is no informal assessment.

Moderate-or-severe neurodevelopmental disability defined as:

Diagnosis of motor impairment: cerebral palsy with functional impairment corresponding to a GMFCS ≥ 2 , but it is not necessary that a GMFCS grading is available from the health care records)

Diagnosis of visual impairment: defined as moderate reduced vision or worse (blind in one eye with good vision in the contralateral eye or blind or can only perceive light or light reflecting objects).

Diagnosis of hearing impairment: defined as hearing loss corrected with aids or some hearing loss not corrected by aids or no useful hearing even with aids.

Cognitive impairment:

- Bayley-III/IV cognitive score < 85 (1st priority)
- Any developmental assessment $< -2SD$ (including the PARCA-R) (2nd priority)
- If none of the above are available, blinded assessment of health care records from 12 months of corrected age and onwards concluding that the child has a cognitive impairment equivalent to moderate or-severe neurodevelopmental disability (3rd priority).

Informal assessment of moderate-or-severe NDD

When there are no relevant health care records from corrected age 18-30 months the records will be accessed by a the blinded assessor and all health care records from corrected age 12 months and onwards will be informally assessed to conclude whether or not the child has moderate-or-severe neurodevelopmental disability.

Prioritisation and possible substitution of data will be done centrally.

Appendix B: Classification of NDD based on parental questionnaire (in cases where components of the co-primary outcomes are unknown or if it is not possible for the blinded assessor to assess NDD based on the health care records):

YES to cerebral palsy: A doctor has said the child has cerebral palsy
 The child CANNOT walk independently at two years of age

NO to cerebral palsy: A doctor has said the child has cerebral palsy

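### Section 2.7 asks the principal investigator, with no blinding condition, for the informal disability judgement that Appendix A gives to the blinded assessor; the order of questionnaire and informal assessment is also not stated consistently

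*Combined protocol and SAP*

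**What the plan says.** Section 2.7 (Data extraction) opens with a general rule: "All data extraction from health care records and data entry into the e-CRF will be done by an assessor who is blinded" to group allocation. The disability outcome is built first from records at 18–30 months' corrected age. Where formal assessment of all four components is not available, the central trial unit fills the gaps from the parental questionnaires. The next step begins: "If answers from parental questionnaires are not available, either the PI will be contacted by the central trial unit". The instruction is that "the PI will be contacted by the central trial unit and requested to provide an informal assessment" of NDD, based on everything known since 12 months' corrected age. No blinding condition is attached, and the word *either* has no matching *or*. The section then refers to Appendix A for details.

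Appendix A names a different person and a different starting condition: "When there are no relevant health care records from corrected age 18-30 months the records will be accessed by a the blinded assessor", who then judges informally from all records since 12 months. It defines NDD as "positive findings for at least one of the four components or NDD based on an informal blinded assessment of all available information" and no NDD as "no positive findings in any of the four components and no NDD based on an informal blinded assessment of all available information".

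The other sections agree with Appendix A. The Summary (Blinding) and section 2.8 have a blinded co-investigator conduct outcome assessments. Both name the principal investigator (PI) separately, as joint author of a local blinding procedure that the central trial unit approves. Section 2.9 tells units to delegate outcome assessment to a co-investigator who can be blinded. The last line of section 2.4.2 requires a blinded assessor for all outcomes.

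**The concern.** Under section 2.4.1 and Appendix A, an informal classification can by itself make a survivor an event. Section 3 lists informal assessments among the means by which the plan expects this outcome on all 1600 children, so the route is a planned one. It is also the most subjective route, and it is used where other data are scarcest. If some of these calls were made by someone who knows the allocation, errors could run in different directions in the two arms and bias the risk difference. The Bayley co-primary outcome is not affected, because it is taken from the test record.

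A second, smaller matter is the order of sources. If the texts do not agree on whether the questionnaire or the informal assessment comes first, the same child can be classified from different evidence depending on which text is followed.

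**Working it through.** **Who makes the informal judgement**

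| Place | Person | Blinding required for this task? |
|---|---|---|
| 2.7, informal step | PI | Not stated |
| Appendix A, informal step | Blinded assessor | Yes |
| Appendix A, definitions of NDD and no NDD | – | Yes, only a blinded informal assessment counts |
| Summary (Blinding) and 2.8 | Co-investigator, with the PI named separately | Yes |
| 2.9 | Co-investigator; the PI is not mentioned | Yes, someone who can be blinded |
| 2.4.2, last line | Assessor | Yes |

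The first sentence of 2.7 covers extraction from records and entry into the e-CRF. The request to the PI is for a judgement, made to the central trial unit, so that sentence does not clearly cover it. An unblinded opinion obtained under 2.7 would not meet either definition in Appendix A.

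**Which source comes first**

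For cognition there is no conflict. Appendix A ranks the Bayley score first, any other developmental assessment second ("including the PARCA-R) (2nd priority"), and blinded review of records third. This agrees with 2.7 and with section 2.6.3.1.

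The difference lies in the whole-child informal assessment. Take a child with no records from 18–30 months but a complete questionnaire:

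- Under 2.7 the questionnaire fills the components, and no informal step follows.
- Under Appendix A's paragraph the absence of those records calls for the informal assessment; the questionnaire is not mentioned.
- Appendix B's heading brings in the questionnaire when components are unknown, or when the blinded assessor cannot judge NDD from the records. That can be read as assessor first, questionnaire second.

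Appendix A closes by saying that ranking and substitution of sources is handled centrally. That settles who applies the order, but not what the order is.

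**Size**

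The plan gives no figure for this point. It does not give the share of children classified informally, the fraction of calls made by someone aware of the allocation, or how far such a person would shift the call. What follows is an illustration only.

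Inputs from section 3: 800 per arm, 50% event rate, alpha 2.5% (taken as two-sided; the plan does not say), mortality 21%, so survivors = 0.79 × 1600 = 1264. This is a simple two-proportion approximation under no true effect, ignoring site and gestational-age stratum.

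- Standard error of the risk difference = √(2 × 0.25 / 800) = 0.0250.
- Type I error = P(|Z + bias/0.0250| > 2.2414).
- Break-even: a bias of 0.65 points gives 3% (0.00653 × 800 = 5.2 children); 1.43 points gives 5% (0.01431 × 800 = 11.4 children).
- With assumed inputs, bias = 0.79 × share × fraction aware × shift:

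| Share of survivors | Fraction aware | Shift | Bias (points) | Type I error |
|---|---|---|---|---|
| 5% | 0.25 | 5 points | 0.05 | 2.50% |
| 10% | 0.5 | 10 points | 0.40 | 2.7% |
| 20% | 0.5 | 20 points | 1.58 | 5.6% |
| 20% | 1 | 20 points | 3.16 | 16.4% |

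The last row needs every input at its assumed maximum.

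**The case against.** The strongest reply is that the documents nearly settle the matter themselves. The PI is given this task once, in a visibly incomplete sentence. That section begins with a blinding rule and ends by pointing to Appendix A, which counts only blinded informal assessments, and local blinding procedures need central approval. This stands, and it makes a drafting slip the likeliest explanation. It does not remove the instruction, because the central trial unit is the body told to contact the PI.

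A reader might infer that the trial planned unblinded adjudication. The documents do not support that: nowhere do they say that PIs know the allocation, and every other statement on assessing this outcome requires blinding. Nor does section 2.9 show that the PI and the assessor are different people, since it does not mention the PI. Only the Summary and section 2.8 name both roles.

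A reader might also infer that a child with records from 18–30 months, one unknown component, nothing positive and no questionnaire ends up missing under Appendix A. That takes its condition (*when* there are no such records) to mean *only when*, and lets its silence override 2.7. The rule itself, "Unclassifiable = if one or more components are unknown and none are positive and there is no informal assessment", allows for an informal assessment in a child with unknown components, and 2.7 orders one for exactly this child. Read together, the texts classify the child. It is still worth saying so outright, because Appendix B's rule for children who cannot be classified leaves out the informal-assessment exception.

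Finally, the bias figures rest on assumed inputs and are not evidence that bias will occur. That is accepted.

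**Conclusion.** The contradiction over who makes the informal judgement is real and should be corrected: section 2.7 names the PI without a blinding condition, and Appendix A requires a blinded assessor. The order of questionnaire and informal assessment for a child with no records from 18–30 months is a smaller inconsistency that the texts leave open.

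Confidence is high for the mismatch in wording. Whether any bias would follow is unknown, and its size cannot be derived from the documents. Over most of the assumed range the effect on type I error is negligible to small. The case for change rests on the contradiction in a subjective step of a co-primary outcome and on how easily it is removed.

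**What to change.** 1. Reword section 2.7 so that the request may go via the PI but the blinded assessor makes the informal judgement, as Appendix A requires. Complete or delete the *either*.
2. State one order of sources and one trigger for the whole-child informal assessment, in identical terms in section 2.7 and Appendices A and B. The sponsor should choose the order before the analysis. Records, then questionnaire, then informal assessment would follow 2.7, but Appendix B's heading can be read the other way, so the choice needs to be explicit.
3. Say expressly that a child with records from 18–30 months, an unknown component, nothing positive and no questionnaire goes to the blinded informal assessment, as 2.7 already implies. Bring Appendix B's rule for unclassifiable children into line.
4. Optionally, record for each informal classification whether the assessor was blinded. The e-CRF is not part of the documents, so such an item may already exist.

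The cost is a few sentences and at most one recorded item. No extra staff are needed, because section 2.9 already has each unit delegate assessment to a co-investigator who can be blinded.
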